4.3 Masking/Blinding of Study

This is an open, randomized trial. Subjects and study team members will not be blinded.

4.4 Storage

The GridION sequencing instrument will be located in [name] lab. The device will only be accessible by study staff.

4.5 Cleaning/Sterilization Procedures (optional)

DNA extraction and sequencing library preparation will be performed in a UV biosafety cabinet category 2 hood to ensure sterile conditions throughout the library preparation steps. Prior to sequencing Flush Buffer will be loaded into the ONT R9.4.1 flow cells in order to remove the storage solution prior to use. To ensure that no cross-contamination occurs, a new, sterile flow cell will be used for each patient.

5 Study Procedures

5.1 Enrollment Visit

At the time of enrollment, the informed consent will be reviewed with the participant and informed consent will be obtained.

Consented patients will be de-identified in compliance with the Health Insurance Portability and Accountability Act of 1996 (HIPAA) and patient identifiers will be stored electronically with access limited to members of the research team on a need-to-know basis. Patient demographics and baseline collection information will be gathered from the participant's medical record and documented in the Medidata Rave database. Demographics and baseline collection data collection will include age, sex, indication for surgery, ASA, major comorbidities, pre-operative biliary stenting/manipulation, and pre-surgical cholangitis, etc.

5.2 Sample Collection Visit

Following enrollment procedures, 2 cc of residual bile collected during surgery will be aliquoted into cryovial and placed on ice (not frozen). It will be picked up by the study team at the time of collection for ONT sequencing. Tissue Request Acquisition Group (TRAG) approval will be requested for managing of samples. The sample will be aliquoted from the clinical collection and so collection will not add additional time to the surgery procedure. Participants will be randomized in Medidata Rave to a study arm based on operation type and pre-operative biliary stenting using a dynamic stratification. Participants will be randomized in a 1:1 ratio.

5.3 Follow up Data Collection

Outcomes will be abstracted from the medical record for 90-days post-operatively and will include outcomes of primary endpoints that include: duration of perioperative antibiotic regimen, total number of antibiotics administered, and administration of broad-spectrum antibiotics vs narrow-spectrum antibiotics. Secondary endpoints will include SSI rate, SSI severity (superficial, deep, organ/space, bloodstream, or urine), and total hospital costs. Standard post-pancreatectomy surgical outcomes will also be collected including: total hospital length of stay (days), ICU length of stay (days), need for and type of interventional procedures, pancreas-specific complications (pancreatic leak/grade, delayed gastric emptying, and post pancreatectomy hemorrhage) hospital readmission, and death. In addition, all culture results and ONT sequencing results will be captured and compared. Additional clinical data will be gathered if deemed appropriate for outcome analysis. Patients will be assigned a study identification number at the beginning of the study to aide in securing identifiable patient information. All patient information will be stored in a secure Medidata Rave database that

will be accessed by designated study members only. Statistical analysis will be performed to compare outcomes between study arms as described in analysis section of this application.

6 Statistical Plan

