2.2 Primary Objective

To improve antibiotic stewardship (reducing duration of peri-operative prophylactic antibiotic regimen, reducing administration of broad-spectrum antibiotic) by providing surgical team with rapid ONT sequencing data in the early post-operative setting.

Success Criteria: Significantly reduced antibiotic regimen duration and use of broad-spectrum antibiotics, corrected for key co-variates ($p<0.1$).

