2.2 Primary Study Endpoints

- Reduced administration of antibiotics with a non-significant ($p>0.05$) effect on SSI rate

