6.1 Sample Size Determination

Data for power analysis based on pilot study data (IRB# 19-011419). Power analysis is based on improvement in antibiotic stewardship with the following assumptions:

- Treatment groups are random and independent
- Microbial detection positivity rate using standard cultures = 54%
- Microbial detection positivity rate using nanopore sequencing = 77%

Analytical method:

- Sample size per group = 66 (total N = 132), Target size=70 per arm, total N=140
- Power = 80%, alpha (type I error) = 0.05, beta (type II error) = 0.2

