6.2 Statistical Methods

Descriptive Statistics

The primary analysis of this study will be a modified intention to treat analysis (ITT), performed to determine how use of ONT changed patient treatment, i.e. did use of ONT improve antibiotic stewardship. Proportions of patients with detection of microbes of interest will be estimated along with exact 95% binomial confidence intervals. Comparisons of the proportions between the two study arms will be compared using Fisher's exact test or Chi-square test as appropriate. We will calculate the time from randomization to first microbial detection within a patient. We will report the mean difference in time to first microbial detection within 96 hours post randomization in both treatment arms, together with a 95% confidence interval. Comparison of time to first microbial detection within 96 hours post randomization, will be performed using Wilcoxon rank sum test or two sample t-test as appropriate. If there are any baseline imbalances in demographic or clinical variables between the two groups, we will perform the analysis using univariable and multivariable linear regression adjusting for these variables with imbalances as possible confounders. Duration of antibiotics, total number of different antibiotics, and broad-spectrum antibiotics vs narrow-spectrum antibiotics administered in the two arms will be compared to determine if use of ONT improved antibiotic stewardship by significantly reducing the duration of perioperative antibiotics and use of broad-spectrum antibiotics

Secondary analysis will evaluate SSI's will be evaluated and classified using ACS NSQIP definitions and data collected will include mortality rate, SSI incidence rate, ICU length of stay, total length of hospital stay, need for interventional procedures, and hospital readmission. Statistical analysis will be performed by the study team to determine if use of ONT significantly improved patient outcome compared to patients who received standard of care

only. The secondary endpoint of the study is a binary endpoint i.e. whether patients develop SSI (yes, no). Association between the secondary outcome and predictor variables will be assessed using univariable and multivariable logistic regression.

In both primary and secondary analysis, the following variables will be assessed for inclusion in the regression models

- Age at time of surgery DOB
- BMI at time of surgery RAVE calculate
- Sex

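### The primary success rule is stated inconsistently (two measures jointly, one unnamed measure plus an SSI condition, or three listed endpoints; level 0.1 or 0.05), so the same data can pass or fail

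*Combined protocol and SAP*

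**What the plan says.** Four current parts of the document describe what decides the trial.

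- **Primary Objective (Section 2.2).** The success criterion is "Significantly reduced antibiotic regimen duration and use of broad-spectrum antibiotics, corrected for key co-variates", at p below 0.1. Two measures are joined by *and*.
- **Primary Study Endpoints (also numbered 2.2).** The single entry is "Reduced administration of antibiotics with a non-significant ($p>0.05$) effect on SSI rate". It does not say which measure of administration is meant, and it adds a condition on SSI that the objective lacks.
- **Follow up Data Collection (Section 5.3).** This refers to "outcomes of primary endpoints that include: duration of perioperative antibiotic regimen, total number of antibiotics administered, and administration of broad-spectrum antibiotics vs narrow-spectrum antibiotics". That is three measures, the second of which is not in the objective. The section gives no order or combining rule and refers the reader to the analysis section.
- **Statistical Methods (Section 6.2).** Within the primary analysis, "Duration of antibiotics, total number of different antibiotics, and broad-spectrum antibiotics vs narrow-spectrum antibiotics administered in the two arms will be compared". The same sentence ends by defining improved stewardship as "significantly reducing the duration of perioperative antibiotics and use of broad-spectrum antibiotics", the pair in the objective. The paragraph also compares detection proportions and time to first detection, although Section 2.3 lists timeliness as secondary.

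The level also differs. Section 6.1 has "Power = 80%, alpha (type I error) = 0.05, beta (type II error) = 0.2". The Patient Follow-up and Safety Monitoring text speaks of one primary outcome, in the singular, at p below 0.05. No part gives a hierarchy, a multiplicity adjustment or an explicit co-primary statement.

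**The concern.** A success rule should give one verdict for any set of results. Here the verdict can depend on which section is cited. The trial is open (Section 4.3). Section 6.2 has the study team carry out the outcome comparisons, with a statistician brought in only for work beyond its abilities, although the Data Processing text in Section 8.3 does mention a qualified statistician. Nothing else in the plan would stop the choice of rule being made after the results are known.

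Split results are foreseeable from the design. A negative sequencing result acts mainly on duration, a positive one mainly on the choice and breadth of agents, and under General Design culture-positive patients in both arms have the same planned course length. The measures need not move together.

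**Working it through.** **1. The plan's own figure.** Inputs from Section 6.1: 54% and 77% positive, alpha 0.05, power 80%, equal arms. With mean proportion (0.54 + 0.77)/2 = 0.655, the usual two-sided formula gives

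n = [1.960 × √(2 × 0.655 × 0.345) + 0.842 × √(0.54 × 0.46 + 0.77 × 0.23)]² / 0.23² = (1.318 + 0.549)² / 0.0529 ≈ 65.9, so 66 per arm.

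The stated 66 reproduces. The quantity being powered is microbial detection, which is none of the antibiotic measures.

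**2. One data set under each rule.** Suppose duration falls with p=0.03, broad-spectrum use has p=0.30 and SSI has p=0.60.

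| Source | Verdict |
|---|---|
| Primary Objective | Failure: 0.30 exceeds 0.1 for the second measure |
| Section 6.2, closing words | Failure: the second measure is not significant at 0.05 or 0.1 |
| Primary Study Endpoints | Can be met, if duration is taken as the measure; the SSI p-value exceeds 0.05 |
| Section 5.3 | Undetermined: no combining rule |

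Separately, if both measures fall with p-values between 0.05 and 0.1, the objective's criterion is met at its own level and missed at the level in Section 6.1.

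**3. Error if Section 5.3 were read as any-of-three.** Success means a reduction, so the relevant error is a false result in the favourable direction: alpha/2 for one two-sided test, that is 2.5% at 0.05 and 5% at 0.10. For three independent tests it is 1 − 0.975³ = 7.3% and 1 − 0.95³ = 14.3%. The documents give no correlation between the measures, so equal correlations were assumed and 1,000,000 draws of three normal test statistics simulated:

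| Assumed correlation | 0.05 per test | Multiple of 2.5% | 0.10 per test | Multiple of 5% |
|---|---|---|---|---|
| 0 | 7.3% | 2.9 | 14.3% | 2.9 |
| 0.5 | 6.3% | 2.5 | 11.8% | 2.4 |
| 0.8 | 4.9% | 2.0 | 9.2% | 1.8 |
| 0.9 | 4.2% | 1.7 | 8.0% | 1.6 |

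Counting significant results in either direction roughly doubles the percentages (12.5% and 23.6% at correlation 0.5), but half of those would show harm, not success.

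**4. Error and power under the joint rule.** With two measures and both required, the false favourable rate at correlation 0.5 is about 0.5% (0.05 per test) or 1.2% (0.10). There is no inflation. The cost is power. Assume 80% for each measure. Joint power is then 0.8 × 0.8 = 64% if independent, 69% at correlation 0.5 and 73% at 0.8 (bivariate normal). Exactly one measure succeeds in 2 × (0.80 − joint power): 2 × (0.80 − 0.64) = 32% at correlation 0 and 2 × (0.80 − 0.729) = 14% at 0.8. Those are the trials in which the stated rules can disagree.

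**The case against.** The best defence is that the plan does contain a coherent rule. The Primary Objective and the end of the primary paragraph in Section 6.2 name the same two measures and join them with *and*. Section 5.3 is a list of items to abstract from the record, and it defers to the analysis section. The study is also labelled a pilot.

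Much of this stands. A reader might infer from Section 5.3 that success on any of the three measures would do, and hence that the plan carries two to three times its stated error. The documents do not support that: no section adopts an any-of rule, and the multiple depends on an assumed correlation. Nor do they support counting detection proportion and time to detection as two further routes to success. Section 6.2 tests them but does not make them success criteria.

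The defence does not dispose of the Primary Study Endpoints section. That section is not a data-collection list, it names no measure, and it carries an SSI condition found in neither the objective nor Section 6.2. The defence also leaves the two significance levels unreconciled, and the number of antibiotics is called a primary endpoint without a role. The pilot label does not help, because the plan sets a formal success criterion and a formal alpha and power.

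**Conclusion.** The concern holds as an inconsistency in the stated success rule. A fall in duration alone fails the Primary Objective but can satisfy Primary Study Endpoints, and the level is 0.1 in one place and 0.05 in two others. That conclusion needs no assumption.

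The error figures in step 3 apply only if Section 5.3 is read as any-of-three, and they depend on the assumed correlation. Under the joint rule, which the objective and Section 6.2 favour, the issue is power: about 64% to 73% for correlations of 0 to 0.8 if each measure had 80%. That 80% is itself an assumption, since Section 6.1 powers neither measure.

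**What to change.** State one primary success rule, in the same words, in the Primary Objective, Primary Study Endpoints, Section 5.3 and Section 6.2, at one stated two-sided alpha. Bring the level in the safety monitoring text and Section 6.1 into line with it. That 0.05 reproduces 66 per arm does not settle the choice, because that calculation is for detection.

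The smallest change is to adopt the rule already in the objective and Section 6.2: duration and broad-spectrum use are co-primary, both must be significantly reduced, and no alpha split is needed. Total number of antibiotics, detection proportion and time to detection then become secondary. If the sponsor prefers, a pre-specified fixed sequence starting with duration is an alternative, but letting duration alone decide sets a lower bar than the current objective. Either way, say explicitly whether the SSI condition is part of the rule, so that it is not dropped by default.

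This is a change of wording, using measures already collected. It should be settled before further between-arm results are examined, since the monitoring text has outcomes assessed every two weeks. The downside of the joint rule is that a reduction in duration alone is not a success, and that power for the pair is below that for either measure. The sample-size section should acknowledge this.

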Since the introduction of our standardized approach, we have improved antibiotic tailoring by developing methods of increasing detection of anaerobic species through our use of bile aspirate in addition to collection of bile swabs³⁸. However, similar to other institutions, it takes an average of 4 days for final bacterial culture results to be generated⁴⁴, and the majority of cultured microbial species have been found to exhibit multi-resistance phenotypes. This means that for the first 4-days post-surgery many of our patients at risk of developing SSI are receiving suboptimal antimicrobial therapy. This provides potential pathogens a window of opportunity to grow and propagate prior to introduction of tailored antimicrobial therapy. Rapid methods of detecting microbial species and antimicrobial resistance phenotypes are required to shorten this window of opportunity. Our data shows that in patients with positive bile cultures it took an average of 7 days to complete microbial identification and AST for bacterial and fungal species (range = 3 – 24 days), and it took 24 days to confirm the absence of biliary microbes (5 days for aerobic cultures, 14 days for anaerobic cultures, 24 days for fungal cultures). In particular, delays in detecting *Candida* species, was of concern due to the increased risk of SSI in patients with biliary candidiasis⁴⁵. In our own patient cohort, 17% of patients were positive for biliary candidiasis, and the microbe was the presumptive cause of 22% of SSIs. In patients with biliary candidiasis, it took an average length of 4.6 days for fungal identification, and an additional 6 days for anti-fungal susceptibility testing to be complete. As anti-fungals are not part of the recommended perioperative prophylactic antimicrobial treatment course, it meant that during the first 2 weeks post-surgery these patients were at increased risk of SSI due to untreated biliary candidiasis.

A single diagnostic test that would enable simultaneous identification of bacterial species (aerobic, anaerobic, fastidious), fungal species, and antimicrobial resistance in an expedited

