Pancreaticoduodenectomy, % (n)	79 (33)	42.9 (18)	35.7 (15)	
Biliary instrumentation, % (n)	52 (22)	52.4 (22)	0 (0)	<0.0001
Vascular reconstruction, % (n)	38 (16)	31.0 (13)	7.1 (3)	0.0079

BMI, body mass index; IQR, interquartile range

Comparison of our optimized ONT sequencing protocol SC results revealed that our ONT protocol had identified 100% of biliary microbial contamination cases, detected 75% of cultured bacterial species and 76% of cultured fungal species, and predicted 81% of antibiotic resistance phenotypes observed using SC results ^{44,48}. With regards to detection of common biliary pathogens ^{3,54-57}, our ONT protocol improved detection of biliary candidiasis, detected 100% of cases of biliary *Escherichia coli* and biliary *Klebsiella*, and detected 83% of biliary *Enterobacter*, 76.5% of biliary *Enterococcus*, 93.8% of biliary *Streptococcus*. However, ONT did not detect one case of *Pseudomonas* infection and one case of *Staphylococcus aureus*, indicating as proposed in this study that SC techniques should be run alongside ONT protocols to ensure that no microbial species are missed. As for detection of pathogens of high clinical concern (i.e. ESBL, CRE species), ONT similar detection rates compared to SC, and potentially improved detection of *E. coli*, *K. oxytoca*, *K. pneumoniae*, and *Citrobacter freundii*. Overall, ONT improved detection of microbial species (particularly with regards to anaerobic species and fungal species) and predicted a significantly higher number of antibiotic resistance phenotypes than were identified using SC. Significantly, the results turnaround for ONT sequencing was just 14 hours compared to an average turnaround time of 98 hours for SC. On average, it took 4.8 days (range = 1 – 15 days) to complete microbial identification and an additional 2 days (range = 0 – 9 days) to complete AST for the culture positive samples. Delays greater than 5 days in completing microbial identification occurred in samples with multiple aerobic species of the same genus (*Enterococcus* spp., *Klebsiella* spp., *Streptococcus* spp.), anaerobic species (*Schaalia (Actinomyces) turicensis*, *Finegoldia magna*, *Veillonella* sp., *Actinomyces johnsonii*, *Parvimonas micra*), and/ or fungal species *Saccharomyces cerevisiae*, *Candida* spp.), and on average, optimal antimicrobial therapy was delayed for 7 days. Use of a test that would enable microbial identification and prediction of AMR phenotypes within 24hrs post-surgery, would, therefore, have significantly shortened the delay in patients receiving optimized tailored antimicrobial therapy post-surgery.

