ONT results different from SC	Adjust and/or narrow antibiotic therapy to cover pathogens found in ONT results, excluding those deemed clinically insignificant. SC results to only be considered in the event of treatment failure with antibiotic therapy targeted towards ONT results.

Databases Used

For the analysis of our endpoints, we are relying on sequence homology for two main tasks, mainly, (1) the identification of species and (2) identification of AMR phenotypes. For species identification, we use the refseq genome database (downloaded on 12/18/2020) with all data from the following higher order taxa groups included: human, protozoa, viral, bacterial, and fungal. For the identification of AMR phenotypes, we use the ResFinder database (downloaded on 06/04/2021, version 4.1) which contains the acquired chromosomal resistance genes, ensuring we know which species is carrying a given resistance gene. For plasmid AMR gene identification, we will use the PlasmidFinder-specific database (downloaded on 7.14.2021/version 2.0.1) and the CARD data (downloaded on 07/07/21, version CARD 2020). These databases undergo regular updates since they were first developed. To ensure the analysis remains consistent throughout the study, databases will not be updated for the duration of the study. In the unlikely event that we require a software/ database update in order to run these tools (compatibility issues with future institutionally required OS update, inability to restore databases from archives after computational disaster), we will validate any newer versions of the database and/or algorithms using the data and culture gold standards from our published study and recently collected data and will only proceed if we have comparable performance in accuracy for species and AMR identification.

Patient Follow-up and Safety Monitoring

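### The stewardship measures reward less or narrower antibiotic, and no planned analysis checks whether the regimen was active against the organisms cultured from the bile

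*Combined protocol and SAP*

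**What the plan says.** Section 5.3 (Follow up Data Collection) lists the primary outcomes as "duration of perioperative antibiotic regimen, total number of antibiotics administered, and administration of broad-spectrum antibiotics vs narrow-spectrum antibiotics". Section 6.2 (Statistical Methods) compares these between arms and treats improvement as "significantly reducing the duration of perioperative antibiotics and use of broad-spectrum antibiotics". The success criterion in 2.2 (Primary Objective) matches: "Significantly reduced antibiotic regimen duration and use of broad-spectrum antibiotics, corrected for key co-variates", at p<0.1. Section 2.2 (Primary Study Endpoints) adds one condition: "Reduced administration of antibiotics with a non-significant ($p>0.05$) effect on SSI rate".

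On culture against sequencing, 5.3 says only that "all culture results and ONT sequencing results will be captured and compared". This is not listed as an endpoint and is not linked to the drugs the patient received.

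The rationale is wider than these measures. Section 1.1 (Background) says that "for the first 4-days post-surgery many of our patients at risk of developing SSI are receiving suboptimal antimicrobial therapy". Section 1.4 reports an average seven-day delay to optimal therapy in the pilot. Section 1.5.3 (Potential Benefits) counts an optimal regimen, for patients who need treatment, as part of stewardship.

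For a sequencing result that differs from culture, Tables 3 and 5 say: "Adjust and/or narrow antibiotic therapy to cover pathogens found in ONT results, excluding those deemed clinically insignificant". They bring culture in only on treatment failure. Section 1.4 reports that in the pilot sequencing "detected 75% of cultured bacterial species and 76% of cultured fungal species, and predicted 81% of antibiotic resistance phenotypes" seen with standard culture.

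**The concern.** A measure that counts only days, number of drugs and breadth improves when an unnecessary drug is stopped. It can also improve when a needed drug is stopped. If therapy is narrowed to the sequencing report and that report lacks an organism that culture later grows, the narrowing may count in favour of Arm 2. Conversely, an antifungal correctly started early for *Candida* gains nothing on these three measures. A positive primary result therefore could not, by itself, separate better stewardship from under-coverage. The step that is meant to link faster results to fewer infections, time on active therapy, would also go unmeasured.

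**Working it through.** **1. The plan's own figures.** Table 2 reproduces the detection rates in the text of 1.4: *Enterobacter* 5/6 = 83.3%, *Enterococcus* 13/17 = 76.5%, *Streptococcus* 15/16 = 93.8%. The sample size in 6.1 also reproduces: 54% against 77%, two-sided alpha 0.05, 80% power, no continuity correction gives

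n = [1.960 × √(2 × 0.655 × 0.345) + 0.842 × √(0.54 × 0.46 + 0.77 × 0.23)]² / 0.23² = 65.9, so 66 per arm.

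That calculation compares detection rates. It gives no input for sizing a coverage measure, so none is sized here.

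**2. Organisms cultured but not sequenced (Table 2).** Misses = culture-positive minus positive by both tests.

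| Organism | Culture | Both | Missed |
|---|---|---|---|
| *Enterococcus* | 17 | 13 | 4 |
| *Serratia marcescens* | 3 | 1 | 2 |
| *Enterobacter* | 6 | 5 | 1 |
| *Streptococcus* | 16 | 15 | 1 |
| *Pseudomonas* | 1 | 0 | 1 |
| *Staphylococcus aureus* | 1 | 0 | 1 |
| *Citrobacter freundii* | 4 | 3 | 1 |
| **Total** | | | **11** |

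The *E. cloacae* miss (5 against 4) is counted within *Enterobacter*, and *P. aeruginosa* within *Pseudomonas*.

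**3. From organisms to patients.** The denominator is the 23 of 42 culture-positive patients in 1.4. The table does not show which misses share a patient, so only bounds follow:

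- Full overlap: the largest single-organism count, 4/23 = 17.4%.
- No overlap: the sum, 11/23 = 47.8%.

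The lower figure is a firm minimum for the pilot sample. The upper figure covers tabulated organisms only.

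**4. Does the SSI condition compensate?** Inputs: 70 per arm (6.1) and a control rate of 21.4% (the pilot's 30-day rate, 9/42, in 1.4). The Arm 2 rates are assumed. The table gives the exact binomial probability that a two-sided Fisher test returns p>0.05.

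| True Arm 2 SSI rate | Condition met |
|---|---|
| 26.4% | 0.93 |
| 31.4% | 0.79 |
| 36.4% | 0.57 |
| 42.8% | 0.27 |

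The pilot had two further infections, at days 34 and 42. A control rate of 11/42 = 26.2% changes the 10-point result only to 0.80.

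**5. Which discordance rule governs?**

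- Tables 3 and 5: culture is considered only on treatment failure.
- Section 1.5.2 (text) and the Arm 2 description in 2.1: therapy is adjusted to, or guided by, culture. Section 1.5.2 also has a sentence tying culture's priority to treatment failure.
- The text before Table 5: if culture grows, reverting to standard practice is an option for the clinician.

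Under the first rule a mismatch can last until treatment fails. Under the second it lasts until culture reports, on average 98 hours (1.4), and those days on a narrowed regimen still count towards narrower use.

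**6. Which measure rewards narrowing?** Section 2.1 gives culture-positive patients in both arms a full 10-day course, so if that text is followed a missed organism need not shorten duration. The number of different antibiotics can rise with a switch and again with a later correction. The broad-versus-narrow comparison is the one that clearly rewards narrowing.

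**The case against.** The strongest reply is that an organism absent from the sequencing report is not a patient without cover. In the pilot, sequencing flagged every culture-positive patient as positive. Bile is often polymicrobial, so therapy aimed at the other organisms may cover the missed one. Nor do the documents show that the starting prophylaxis covered *Enterococcus*, which alone sets the 17% minimum, so there may have been no cover to lose. All of this stands.

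A reader might carry the pilot bounds into Arm 2: 0.54 × 70 = 37.8 culture-positive patients, times 17.4% and 47.8%, or about 7 to 18 patients whose loss of cover would score as a gain. The documents do not support that reading. If the pilot bounds carried over, those would be patients with a cultured organism missing from the sequencing result, and nothing more. Nor is 48% a ceiling: Table 2 lists selected organisms, and detection across all cultured species was only 75–76%.

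The plan also has safeguards: the SSI condition, the stopping rules in Table 7, and the text that lets culture guide therapy. They limit harm, but none measures coverage; the SSI condition is weak by the calculation above, and the culture text is contradicted by Tables 3 and 5.

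A reader might further infer that the trial cannot show its hypothesised benefit. That goes too far. Timeliness of sample analysis and SSI are secondary endpoints, and 6.2 analyses time to first detection and SSI, so a benefit from earlier treatment could appear there. Only the step between them is missing.

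**Conclusion.** The gap is real and should be fixed. Stewardship is scored by shorter, fewer or narrower antibiotics, while the protocol's own account of it includes an optimal regimen, and no analysis looks at activity against cultured organisms. In the pilot, between 4 and 11 of 23 culture-positive patients (17% to 48%, tabulated organisms only) had a cultured organism absent from the sequencing result. This is the group at risk of lost cover; the share actually uncovered is unknown, which is the reason to measure it. How far the risk carries into the trial depends on which discordance rule governs, and the documents do not settle that. The 79% figure for the SSI condition rests on 70 per arm, a 21.4% control rate, an assumed 10-point rise and a two-sided Fisher test. The missing measure does not invalidate the planned comparison of antibiotic use; it limits what a positive result can be taken to mean.

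**What to change.** Add to 5.3 and 6.2 a secondary measure, scored by the same rules in both arms against final culture and susceptibility results:

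- the proportion of culture-positive patients with at least one cultured bacterial or fungal organism not covered by the regimen in use at 48 h, and again at 96 h, after surgery;
- uncovered days to day 10.

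Report the arm difference with a 95% CI beside the primary result, and give it to the DSMB. State in advance how to score isolates without susceptibility results and organisms deemed clinically insignificant. Record antibiotics by drug and date, since 5.3 names only duration, number and spectrum. Do not make the measure a gate on the primary claim: without a threshold it would repeat the weakness of the SSI condition. Separately, reconcile Tables 3 and 5 with the text of 1.5.2 and 2.1 on discordant results. The measure does not set which therapy to use.

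The cost is SAP wording and a modest amount of chart abstraction and scoring across 140 patients. There are two downsides to state. Organisms seen only by sequencing earn no credit. And Arm 1 therapy is tailored to the same culture that serves as the yardstick, so comparisons after culture reports favour Arm 1; the 48 h comparison is the cleanest.
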